7.5.2 Biopsy and resection specimen handling and pathologic analysis

All biopsies and all freshly resected tumor specimens at UW will be taken immediately to the surgical pathology suite adjacent to the operating room. The specimen will be inked in order to provide subsequent pathologic evaluation of presence or absence of residual tumor at the resection margins. The specimen will then be serially sectioned with submission of the appropriate tissue for permanent, paraffin embedded sections to ensure accurate pathologic analysis of resection margins, as well as high-quality hematoxylin and eosin stained sections for morphologic analysis of the tumor and for evaluation of necrosis, apoptosis, and any inflammatory infiltrate. These sections also will be assessed by immunohistochemical analysis for the presence of CD4 and CD8 positive T cells, NK cells (CD56 and CD16), and macrophages (CD68) (the antibodies for which all function well on formalin-fixed tissues).

7.5.3 Handling of fresh tissue samples.

The remaining unfixed tissue will be divided into specimens that will be sent to our research lab for derivation of autologous cultured tumor cell lines and bulk tumor lysate (for use as pulsed antigen for *in vitro* immunologic assays), and tissue that will be frozen in OCT for frozen sections or cryopreserved for pilot molecular studies. The standard protocol for frozen section analysis will include assessment of activation markers on infiltrating T cells (CD69) and for evidence of regulatory T cells (CD25 and FoxP3) by double immunolabeling with CD3, CD4, or CD8, as appropriate. In addition, we will stain for HLA class I and II to assess changes in HLA level on tumor cells, as enhanced class I expression was noted in the mouse studies. Finally, we will assess the expression of the respective target antigens of these experimental agents (i.e., GD2) on tumor cells before and after study treatment. For all histologic analyses, it is likely that inflammatory infiltrates will be patchy, making precise quantification difficult. Nonetheless, a semiquantitative grading scheme will be developed in order to compare the composition and degree of inflammatory infiltrates between patients and, where possible, in pre- and post-treatment specimens from the same patient.

7.5.4 Quantification of the histologic analyses.

For the primary parameters to be assessed on the resected melanoma (i.e., necrosis, apoptosis, and cellular infiltrate), an objective scoring system will be established by a pathologist, grading each specimen with a score of 0, +, ++, +++. The specific criteria for each category will be determined based on the appearance of specimens from the initially enrolled patients in order to provide a spectrum from which meaningful comparisons can be derived. In addition, purely quantitative assessment of necrosis of tumor cells also will be measured and scored with a value ranging from 0% - 100% of tumor area. These and all pathology analyses will be performed by a pathologist in a non-blinded fashion, but will be repeated, using the scoring system thus established,

by a second blinded pathologist. For quantitation of expression levels of HLA class I and II and the GD2 antigen on a per cell basis, it may be useful to use flow cytometric analyses in addition to attempting to qualitatively compare “brightness” of staining between histologic frozen sections in different tumors. As such, fresh tissue will be disaggregated into a single-cell suspension, and these parameters will be evaluated by flow cytometry where possible.

7.5.5 Additional preliminary analyses.

For select samples that do show a cellular infiltrate, *in situ* hybridization will be performed on frozen sections to determine the expression of intracellular gamma interferon in T cells and NK cells infiltrating into the tumor. Depending upon what is observed, other cytokines may be evaluated selectively by *in situ* hybridization.

7.5.6 For patients with accessible recurrences following completion of protocol therapy, we will attempt to obtain core needle biopsies of the recurrent lesions and apply similar analyses to those previously described.

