9.2 Definition of Study Endpoints

9.2.1 Primary Endpoints

Pathology evaluations of necrosis, apoptosis, and cellular infiltrate:

Pathology evaluations of necrosis, apoptosis, and cellular infiltrate will be performed on a standard scale with 4 categories: "0" (none), "+" (low), "++" (medium), or "+++" (high). These evaluations will be performed independently by two pathologists in a blinded fashion. In the case of a disagreement, the tumor tissues will be evaluated by a third pathologist.

Time to recurrence (duration of remission):

For a given subject, time to recurrence will be defined as the number of days from the day of evaluation following course 2 of IC treatment to the day the subject experiences an event of recurrence or death, whichever comes first. All subjects on this study have disease deemed to be completely resectable, and all subjects are expected to be going into complete remission following surgical resection. Uniformity of follow up time is best provided by clarifying the time after “study evaluability” that recurrence is first identified (and confirmed whenever possible). As such, the time point of “study evaluability” will be designated the day of evaluation following course 2 of IC treatment, when CR is first demonstrated clinically and radiologically. Subjects in Group A and Group B will each have spent equivalent time since study entry in getting to this point: each will have had their surgical resection and their first 2 courses of IC treatment. The only difference is that surgery is before course 1 for Group A and after it for Group B.

If a subject has not experienced an event of recurrence (or death) at the time of analysis, then the subject’s data will be censored at the date of the last available evaluation

Overall survival:

Overall survival will be defined as the number of days from the randomization to the date of the subject’s death. If a subject is alive at the time of analysis, then the subject’s data will be censored at the date of the last available evaluation

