9.3.2 Sample Size/Accrual Rate

The first primary objective of this study is to evaluate the histological evidence of anti-tumor activity of hu14.18-IL2 by comparing pathological endpoints between the two groups after dichotomizing the evaluation of apoptosis, necrosis and cellular infiltrate into *positive* (i.e., the microscopic evaluation is classified as “low”, “medium”, or “high”) or *negative* (i.e., the evaluation is classified as “none”) using Fisher’s exact test. With eight subjects per group, a difference of 70% in the proportions of subjects classified as *positive* for necrosis, apoptosis, or cellular infiltrate between the two study arms will be detected with at least 82% power at a two-sided significance level of 0.1. A difference of 60% will be detected with at least 64%. Smaller differences are unlikely to be detected as statistically significant. The sample size chosen is sufficient to provide accuracy in the estimated rate of subjects classified as *positive*. Specifically, with eight subjects per group, the standard error of the proportions of subjects classified as *positive* necrosis, apoptosis, or cellular infiltrate for each group will be at most 0.18.

The second primary objective of this study is to evaluate the time to recurrence (duration of remission) and overall survival relative to historical control data described in Section 1.3.3. This study is not designed to detect differences in time to recurrence or overall survival between the two study arms. Instead, time to recurrence and overall survival time of both arms combined will be compared to historical controls qualitatively. Time to recurrence and overall survival time will be summarized using point estimates of the median time to recurrence/overall survival time and associated 90% confidence intervals. Furthermore, the two-year recurrence free survival rate and the two-year survival rate will be reported along with the corresponding 90% confidence intervals. The following table gives (two-sided) Wilson’s score 90% confidence intervals for the two-year survival/two-year recurrent-free survival rates, assuming a total sample size of 16 subjects.

Table 9: Ninety percent confidence bounds for two-year survival/two-year recurrent-free survival rates

Observed number of subjects alive/recurrent-free after 24 months	Proportions of subjects alive/recurrent-free after 24 months	Lower 90% confidence limit	Upper 90% confidence limit
2	0.12	0.04	0.32
4	0.25	0.12	0.45

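### The none-versus-any line of the primary histology endpoint is to be set during the trial from early specimens, apparently with arm known; it should be set masked and frozen

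*Combined protocol and SAP*

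**What the plan says.** Section 7.5.4 deals with necrosis, apoptosis and cellular infiltrate in the resected tumour. It says that "an objective scoring system will be established by a pathologist, grading each specimen with a score of 0" up to three plus signs, and then "The specific criteria for each category will be determined based on the appearance of specimens from the initially enrolled patients". The stated purpose is to obtain a range of appearances wide enough to compare. On blinding it says "These and all pathology analyses will be performed by a pathologist in a non-blinded fashion, but will be repeated, using the scoring system thus established", the repeat being done "by a second blinded pathologist".

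Section 9.2.1 describes the same endpoint differently. The evaluations "will be performed on a standard scale with 4 categories" (none, low, medium, high), with no criterion for any of them, and "These evaluations will be performed independently by two pathologists in a blinded fashion", with a third pathologist for disagreements.

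Section 9.3.2 tests the first primary objective "by comparing pathological endpoints between the two groups after dichotomizing the evaluation of apoptosis, necrosis and cellular infiltrate into" positive (low, medium or high) and negative (none), by Fisher's exact test. Section 9.4.4 repeats the test and adds, under the primary endpoints, a McNemar comparison of pre-study biopsy with resected tumour in the arm treated before surgery. Section 9 swaps the A and B labels relative to the Schema, so the arms are named here by timing of surgery.

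**The concern.** The four grades collapse to one line, none against any, and that line is the whole primary histology endpoint. Nothing in the documents defines it in advance, masks the specimens used to draw it, fixes a date after which it cannot move, or says whether those specimens stay in the comparison.

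This is separate from the contradiction between 7.5.4 and 9.2.1 over who reads blinded. If both reads were blinded as 9.2.1 says, the readers would still apply a line that may have been drawn by someone who knew which tumours had been treated. Section 7.5.3 expects infiltrates to be patchy and hard to quantify, so the step from none to low leaves room for judgement.

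At stake are the test, the reported positive rates with their 90% intervals, and the use that section 9.1 makes of histological activity in judging whether further evaluation is warranted.

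**Working it through.** **Inputs from the documents.** 8 subjects per group; Fisher's exact test; two-sided level 0.10; positive means any grade above none (9.3.2, 9.4.4).

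**Not in the documents, so assumed.** How many early specimens set the scale (taken as m = 2, 3 or 4 per arm), that they stay in the 8 v 8 comparison, and an underlying continuous score with the same distribution in both arms.

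**1. The plan's own figures.** Exact enumeration of the two binomials gives power of 81.2% for 10% v 80% positive and 65.7% for 10% v 70%, against the stated 82% and 64%. Over all control rates the minima are 80.0% and 61.4%, so the plan's wording of a guaranteed minimum is slightly strong. The maximum standard error is √(0.25/8) = 0.177, against the stated 0.18. These figures all treat the definition of positive as fixed. With a fixed cut the true two-sided error is at most 2.8%, and about 1.3% in the drug's favour.

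**2. How far one tumour can move the test.** Two-sided Fisher p-values, 8 v 8:
- 1 v 5 positive: 2 × (28 + 448)/8008 = 0.119
- 1 v 6 positive: 2 × (8 + 224)/11440 = 0.041

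Moving one treated tumour across the none/low line turns a non-significant result into a significant one.

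**3. Worst-case inflation of the difference.** Rank the 2m early scores from highest to lowest. With identical arms all C(2m, m) orderings are equally likely. Choose the cut with the largest treated-minus-control count above it.
- Mean of that maximum, cut allowed anywhere: Σ C(2m, m+k)/C(2m, m) for k = 1 to m. This is 5/6 for m = 2, 22/20 for m = 3 and 93/70 for m = 4.
- If at least one early tumour must fall on each side of the cut, subtract the orderings in which controls lead throughout: 1/6, 2/20 and 5/70. This leaves 4/6, 20/20 and 88/70.
- Later subjects are independent of the cut and add nothing on average, so divide by 8.

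| Early subjects per arm | Cut between early tumours | Cut anywhere |
|---|---|---|
| 2 | 8.3 points | 10.4 points |
| 3 | 12.5 points | 13.8 points |
| 4 | 15.7 points | 16.6 points |

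Simulation under the stricter rule (20,000 null trials per setting) gave 8.4, 12.3 and 15.5 points.

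**4. Worst-case false positives.** In the same simulations, rejection in the drug's favour was 2.6%, 3.4% and 4.1% for m = 2, 3 and 4, against about 1.3% with a fixed cut. If the cut is chosen to separate the arms in either direction, total rejection is 4.2%, 6.1% and 8.0%.

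**5. Cut set without regard to arm.** With the cut at the pooled median of the same early specimens, the mean arm difference is about 0 and rejection in the drug's favour is about 1.0–1.6%, close to the fixed-cut figure.

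**The case against.** Four points can be made on the other side.

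- **The scale-setter's blinding is not stated.** A reader might infer that the documents say an unblinded pathologist draws the line. They do not. Section 7.5.4 names only a pathologist, attaches non-blinded to performing the analyses, and 9.2.1 has both reads blinded. Even so, the blinded repeat uses the system already established alongside the non-blinded read, so this remains the plain reading.
- **The early tumours' share of the analysis is not stated.** A reader might infer that they are a large part of the 8 per arm. Section 7.5.4 gives neither their number nor their arm and does not say that they stay in the comparison. The initially enrolled patients could even be the 4 subjects entered before Version 5. The point stands because no sentence settles this, but the sizes above are conditional on it.
- **The aim of 7.5.4 is spread across specimens, not separation of arms.** This is correct, and step 5 shows that such a cut does no harm. It answers the concern only if arm is unknown when the line is drawn.
- **The freedom is limited.** The lowest grade is labelled none, and necrosis is also measured as a percentage of tumour area. But 7.5.4 leaves the criteria for every category open, and the primary test does not use the percentage, which does not cover apoptosis or infiltrate.

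The study is a pilot, and most of its analyses are descriptive. That lowers the stakes but does not supply a definition of the endpoint.

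**Conclusion.** The concern holds as a design weakness. The line on which the primary histology test rests is left to be set during the trial, apparently with arm known, and later blinded reading would not undo that. In the worst case the arm difference is inflated by about 8 to 16 points, and false positives in the drug's favour go from about 1.3% to 2.6–4.1% for each of the three features. This assumes identical arms, a freely movable cut chosen to favour treatment, and 2 to 4 early subjects per arm who stay in the analysis.

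Two stronger readings do not hold. One is that calibrating on trial specimens biases the comparison in itself: without knowledge of arm it does not. The other is that the test would exceed its planned error rate. With up to 4 early subjects per arm every figure stays below 10% two-sided, because Fisher's test is very conservative at this size. Only if 6 or all 8 per arm informed a cut chosen in either direction would it pass 10% (11.6% and 15.2%). The main harm is to the estimated difference.

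**What to change.** Amend section 7.5.4 as follows.

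- The blinded pathologist already planned writes the category criteria, at least the none/low boundary for necrosis, apoptosis and infiltrate. The slides are coded and masked to arm, timing of surgery and pre- or post-treatment status.
- The criteria are dated and frozen before any specimen is scored for the primary analysis.
- Any specimen already read is rescored masked under the frozen criteria.
- Sections 7.5.4 and 9.2.1 are reconciled so that the reads used in the primary analysis are blinded.

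Trial specimens may be used for calibration under this masking. Material outside the comparison may be used if available but is not required; no document says that tissue from the 4 earlier subjects is held. The pre-study biopsies should not be described as outside the primary analysis: they enter the McNemar comparison in 9.4.4. They may also be only fine needle cytology (3.1.11), and 7.5.1 expects extensive infiltrate analysis to be impossible on most of them.

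The cost is protocol wording, slide coding and some rescoring, with no new patients or tissue. Masking may be imperfect if treatment changes are visible under the microscope.

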7.6 Late evaluation for recurrence or late toxicity

The following schedule (Table 8) describes clinical evaluations, lab testing and immunological samplings suggested for subjects following completion of all study treatment, to be evaluating for late effects of the treatment as well as time to recurrence. The exact tests to be ordered will be left to the discretion of the treating physician(s) as they feel appropriate, given each subject’s clinical history and presenting symptoms and signs. Subjects who have recurrence of disease will be followed for survival only.

TABLE 8.
CLINICAL ASSESSMENT GUIDELINES FOR RECURRENCE OR LATE TOXICITY

	2 & 4 months after treatment completion of cycle 3 therapy (months 5 & 7)	Every 3 months (months 10-25)	Every 6 months (starting at month 31)	At time of recurrence¹
Interim complete history and Physical Exam	X	X	X	X
Adverse event assessment	X	X	X	X
Weight	X	X	X	X
Performance Status	X	X	X	X
Tumor Assessment	X²	X²	X²	X^{2,3}
Vital signs (T, BP, P, RR)	X	X	X	X
CBC, diff, plts ⁴	X	X	X	X
AST, ALT, T bili, alk phos, alb, LDH, Na, K, Cl, HCO ₃ ,Cr, BUN, Glucose, Ca, Mg, Phosphate ⁴	X	X	X	X
INR/PTT ⁴	X			X
Urinalysis ⁴	X			X
Biopsy				X⁵

¹ These evaluations will be performed only at the time that disease recurrence is noted. Following this time, subjects will be followed only for survival.

² These evaluations should include CT scans of all areas of known prior metastatic disease. Other examinations can be performed as warranted clinically. If, at any of these evaluations, a potential for recurrent disease is identified, appropriate clinical studies (additional X-rays, scans, and/or lab tests, as clinically indicated) will be performed to identify and localize potential recurrent disease.

³ If recurrent disease is identified clinically or radiologically, efforts should be made to confirm its neoplastic nature by biopsy.

⁴ The exact laboratory tests to be obtained at follow-up visits shall be left to the discretion of the treating physician(s) as they are indicated clinically.

⁵ Recurrence should be confirmed by biopsy whenever possible. If possible and clinically indicated, the biopsy should be a core or excisional biopsy performed at the UWCCC. In doing so, fixed and fresh tissue can be evaluated with the same techniques used to evaluate the surgically resected tissue from this same subject as part of this study.

7.7 Blood drawing totals

All subjects entered into this study will participate in all specified treatment, evaluations, specimen collection and blood testing, with their written consent. A subject may choose to withdraw consent and leave the study at any time. To minimize the amount of blood withdrawn, we will be collecting all required blood tests in pediatric tubes. For Groups A (the subjects who will undergo the greatest degree of monitoring), the blood drawing requirements (utilizing blood sparing microtubes and smallest possible volumes for all clinical tests) for the first 2 courses of treatment for all studies included in Tables 5, 6A, 6B, and 7A are as follows:

Courses 1 and 2 and surgery clinical labs -----	80 ml	
Courses 1 and 2 hu14.18-IL2 PK and serological assays -----	190 ml	Courses 1 and 2
NK/ADCC -----	30 ml	
Courses 1 and 2 T cell studies -----	100 ml	
Total blood for Courses 1 and 2 and surgery -----	430 ml	

As the removal of 480 ml of blood (1 unit) is considered acceptable for individuals > 55 kg, this corresponds to 8.7 ml/kg over this initial 2 month period. The required volume of 430 ml needed for full participation in the first 2 courses of this study is below this limit (7.8 ml/kg). Blood drawing requirements during Course 3 are less than during Course 1 and 2 because there is no need to repeat the “baseline samples” obtained prior to Course 1. Thus, insuring safe blood volumes are obtained for Courses 1 and 2 will insure the same for Course 3. With this level of monitoring, an individual weighing as little as 50 kg could provide sufficient blood and still fall below the limit of 8.7 ml/kg. As such, for any subjects weighing between 45 and 50 kg, we will reduce the volume of heparinized blood collected at the end of Courses 2 and 3 from 50 ml to 10 ml (see Table 7A). This reduces the total blood volume for Courses 1 and 2 to 390 ml, which would allow subjects with weights as low as 45 kg to give less than the 8.7 ml/kg limit. Since the risks from obtaining adequate monitoring blood samples becomes greater in subjects with lower weights, we shall exclude any subject < 45 kg. This is unlikely to exclude any otherwise eligible subjects, as any subject healthy enough to enroll in this study very likely would weigh in excess of 45 kg.

In addition, there is a risk of additional blood loss during the surgical resection that is scheduled as part of this study. It is difficult to anticipate how much blood will be lost from subjects during the resection. Therefore, we will rely upon the hemoglobin concentration (obtained with a CBC) that will be checked regularly in the context of clinical monitoring (see Tables 5, 6A, and 6B) to assess for anemia due to excess blood loss. Subjects whose hemoglobin concentrations fall below the level that is set as an inclusion criterion (i.e., 10 gm/dl) will not receive the next scheduled course of protocol treatment until this parameter is again above 10 gm/dl. As described in Tables 6A and 6B, this test may be repeated as needed until the result meets this inclusion criterion. Upon re-initiation of treatment, to reduce the volume of blood drawn from these particularly susceptible subjects, we will reduce the volume of heparinized blood collected at the end of Courses 2 and 3 from 50 ml to 10 ml (see Table 7A). If recovery of anemia delays the start of the subsequent course of protocol treatment by more than 8 weeks, the subject will not be allowed to receive any further study treatment.

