7.4.2 Anti-hu14.18-IL2 antibody levels

Serum specimens will be obtained at the indicated times shown in Table 7A and cryopreserved. These will then be tested in ELISA assays currently in use (36) and now being developed to detect and quantitate antibody against the hu14.18-IL2 IC molecule.

TABLE 7A.
IMMUNOLOGICAL AND PHARMACOKINETIC ASSESSMENT

	Base Line ¹	Week 1				Week 2	Week 5
DAY		1 ²	2	3	4	8	29(1) ^{2,3}
Hu14.18-IL2		X	X	X			
Serum hu14.18-IL2 levels ⁴		X/X	X/X	X/X			
Soluble IL2 receptor	X	X/C1		X/C1	X	X	X
Anti- hu14.18-IL2 Ab	X	X/C1		X/C1	X	X	X
Red top tubes (mL) ⁴	2x10	2x10/1x10; 3x10	1x10/1x10	2x10/1x10	1x10	1x10¹¹	1x10¹⁰
In vitro NK/ADCC studies ⁵	X					X C2+3	X C2+3
Green top tubes (mL) ⁵	1x10					1x10 C2+3	1x10 C2+3
In vitro T cell studies ^{6,7}	X^{6,7}						X^{6,7} C2+3
Heparinized syringe (mL) ^{6,7}	50						50^{6,7} C2+3
In vivo binding ⁸	X				X		

X/ = pre-IC⁹

/X = post-IC⁹

¹ Studies scheduled for “Baseline” can be obtained at any time from 3weeks prior to randomization until just prior to (within 10 minutes) beginning study treatment.

² Day 29 of each course (+/- 7 days leeway to facilitate clinical scheduling) = day 1 of subsequent course.

³ These tests may be performed up to 1 week prior to initiating the next course of therapy (day 22-29 of current course).

⁴ To better understand the pharmacokinetics of hu14.18-IL2 serum will be obtained from subjects in both groups for all courses to measure hu14.18-IL2 levels at the following times: pre and post the 4 hr IC infusion and again 2, 4, and 8 hours after completion of the 4-hr IC infusion on days 1 and 3; on day 2, only the pre- and post-IC samples will be collected.

- ⁵ *In vitro* testing of NK and ADCC function will be performed on selected patients five times with 10 mL of heparinized blood: at baseline, on day 8 of Courses 2 and 3 (C2+3) and within one week of the end of Courses 2 and 3. Additional lymphocytes obtained at the day 8 time points will be cryopreserved for subsequent DNA analyses.
- ⁶ Lymphocytes will be cryopreserved for subsequent T cell function testing from 50 mL of heparinized blood. Plasma collected with this sample also will be cryopreserved for subsequent immunological assays. This sample will be obtained three times: once at baseline, and within one week of the end of both Courses 2 and 3 (C2+3).

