- ⁷ For subjects weighing between 45 and 50 kg, and for subjects who experience anemia (i.e., documented hemoglobin < 10.0 gm/dl), the volumes of these syringes will be reduced to 10 ml.
- ⁸ Biopsies will be performed during Course 1 only on selected, consenting subjects in Groups A who have readily accessible cutaneous lesions. (Group B is excluded because they will have no detectable disease at this time.) In addition to pilot studies analyzing for hu14.18-IL2 *in vivo* binding, immunohistologic components, including lymphocyte infiltration, target antigen expression, and assessing for T cell responses (including CD8⁺, CD4⁺ and NK phenotypes), will be performed on the biopsy samples. Depending on the number of cutaneous lesions, biopsies will be done at baseline and then once again between days 4-7 (following completion of cycle 1 therapy).
- ⁹ Just prior to (within 10 minutes) starting the infusion and within 10 minutes prior to stopping the infusion, for the 4-hour hu14.18-IL2 infusion, as indicated.
- ¹⁰ Ten ml Red top tube will be obtained on days 8 and 22/29 of each cycle regardless of the protocol therapy to which subject is randomized.

TABLE 7B.

ADMINISTRATION OF HU14.18-IL2 AND BLOOD SAMPLING FOR PK ASSAYS ORGANIZED BY AGENT TO BE ADMINISTERED

Hu14.18-IL2 Only:

	•	•	•	•	•	•	•	•	•	•	•	•	•	•	•	•
Time (h) ¹	0	1	2	3	4	5	6	7	8	9	10	11	12	13	14	
hu14.18-IL2 ³ (4 h)	-----															
hu14.18-IL2 Samples ⁴	X/ pre					/X post		•		•				•		
Sample # ²	IC1.1				IC1.2											

¹ Time is listed with the reference point (i.e., time 0) as the start of treatment on a given day.
² Samples will be labeled with the following information: an abbreviation of the agent “IC” for hu14.18-IL2), an integer representing the day in a given treatment course (day 1 as shown in the table above), a decimal point, and a second integer representing the time point as depicted in the table.
³ Hu14.18-IL2 is given as a 4-hour infusion. ⁴ Hu14.18-IL2 PK samples (10 ml red top tube, 5 ml of serum per sample) are obtained just before (pre) and just at the end of the hu14.18-IL2 infusion (post).

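### Section 7.7's 430 ml blood total does not cover the Table 7A draws it claims to include if red-top tubes hold 10 ml, so the 50 kg and 45 kg statements are not supported as written

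*Combined protocol and SAP*

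**What the plan says.** Section 7.7 gives blood volumes "for the first 2 courses of treatment for all studies included in Tables 5, 6A, 6B, and 7A are as follows". The lines are 80 ml for clinical labs, 190 ml for PK and serology, 30 ml for NK/ADCC and 100 ml for T-cell studies, with a stated total of 430 ml. The limit is 8.7 ml/kg, from one 480 ml unit at 55 kg. The section says of the total: "The required volume of 430 ml needed for full participation in the first 2 courses of this study is below this limit (7.8 ml/kg". It then says "an individual weighing as little as 50 kg could provide sufficient blood and still fall below the limit of 8.7 ml/kg". For subjects of 45 to 50 kg it will "reduce the volume of heparinized blood collected at the end of Courses 2 and 3 from 50 ml to 10 ml", and adds: "This reduces the total blood volume for Courses 1 and 2 to 390 ml". Inclusion criterion 3.1.3 takes its 45 kg minimum from this section.

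On tube size, 7.7 says "we will be collecting all required blood tests in pediatric tubes" and gives no volume. Section 7.4.1 and Table 7B footnote 4 specify a 10 ml red-top tube per PK sample, and Table 7B asks for 5 ml of serum from each.

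The PK schedule is described in three ways:

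- Section 7.4.1: before and after the infusion on days 1 and 3.
- Table 7A tube row: day 1 reads "2x10/1x10; 3x10", which adds three later tubes. Day 2 has a pre and a post tube. Day 3 has no late tubes.
- Table 7A footnote 4: pre, post and 2, 4 and 8 hours after infusion on days 1 and 3, and pre and post on day 2, in both groups and all courses.

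**The concern.** The 430 ml figure supports three safety statements: that 50 kg is heavy enough for full sampling, that a 40 ml cut suffices from 45 to 50 kg, and that 45 kg is a safe entry minimum. The margins are thin: 5 ml at 50 kg and 1.5 ml at 45 kg. If the total omits draws that Table 7A requires, staff who follow that table with the specified tube would exceed the plan's own limit in lighter subjects. These subjects also undergo surgery, with a blood loss that 7.7 says is hard to predict.

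**Working it through.** **1. The plan's own figures.** 480/55 = 8.73, used as 8.7. 430/55 = 7.8. 430/50 = 8.6. 430 − 40 = 390, and 390/45 = 8.67. All the ratios built on 430 reproduce. The caps are 8.7 × 50 = 435 ml and 8.7 × 45 = 391.5 ml, so the slack is 435 − 430 = 5 ml and 391.5 − 390 = 1.5 ml.

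The four lines as extracted add to 80 + 190 + 30 + 100 = 400 ml. That table is visibly broken in the extracted text, so PK plus serology is also tried at 430 − 80 − 30 − 100 = 220 ml.

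**2. The other research lines.** NK/ADCC: 3 × 10 = 30 ml. T cells: 2 × 50 = 100 ml. Both match Table 7A. The non-red-top total is 80 + 30 + 100 = 210 ml.

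**3. PK alone under footnote 4.** (5 + 2 + 5) samples × 10 ml × 2 courses = 240 ml. This exceeds both 190 and 220 ml before any serology tube is counted.

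**4. All red-top tubes, Courses 1 and 2, at 10 ml.** Tubes other than PK: 2 at baseline, 2 second pre-dose tubes (days 1 and 3, read as Course 1 only), and days 4, 8 and 29 in each course (6), making 10. PK tubes: 4 × 2 = 8 under 7.4.1, 9 × 2 = 18 on the tube row, 12 × 2 = 24 under footnote 4. The most favourable reading of the row takes one tube per draw time, merges baseline with day 1, and merges Course 1 day 29 with Course 2 day 1. That leaves 18 PK tubes plus 5 others.

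| Reading | Tubes | Red-top ml | Total (+210) | ml/kg at 50 kg | ml/kg at 45 kg after 40 ml cut |
|---|---|---|---|---|---|
| 7.4.1 schedule | 18 | 180 | 390 | 7.8 | 7.8 |
| Tube row, most favourable | 23 | 230 | 440 | 8.8 | 8.9 |
| Tube row | 28 | 280 | 490 | 9.8 | 10.0 |
| Full footnote 4 | 34 | 340 | 550 | 11.0 | 11.3 |

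If the second pre-dose tubes are also drawn in Course 2, the last two totals rise by 20 ml to 510 and 570. Every Table 7A reading exceeds 435 ml at 50 kg and, after the 40 ml cut, 391.5 ml at 45 kg (400, 450 and 510 ml).

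**5. Where 190 ml may come from.** Take 7.4.1's schedule with the second pre-dose tubes in both courses: days 1 and 3 at 30 ml each, plus 30 ml for days 4, 8 and 29, is 90 ml per course. Then 20 (baseline) + 2 × 90 − 10 (Course 1 day 29 merged) = 190 ml.

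**6. Draw volume that would meet 8.7 ml/kg.** At 50 kg: (435 − 210)/28 = 8.0 ml on the tube row, and 225/34 = 6.6 ml under full footnote 4. At 45 kg with the 40 ml cut: (391.5 − 170)/28 = 7.9 ml, and 221.5/34 = 6.5 ml. At Table 7B's ratio of 5 ml serum per 10 ml tube, 6.5 ml of blood yields about 3.25 ml of serum.

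**7. Without the draws on selected subjects (NK/ADCC and T cell, 130 ml).** Tube row: 80 + 280 = 360 ml, or 8.0 ml/kg at 45 kg. Full footnote 4: 80 + 340 = 420 ml, or 8.4 at 50 kg and 9.3 at 45 kg, with break-even at 420/8.7 = 48.3 kg.

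**The case against.** The strongest reply is the pediatric-tube sentence, which is not restricted to clinical labs. If red-top draws are small enough, everything complies, so a reader who infers that subjects will be overdrawn goes beyond the documents. That stands: they conflict on tube volume and do not settle it. But the sentence gives no volume, and Table 7B's 5 ml of serum cannot come from 5 ml of blood, so it does not rescue the total either. The full NK/ADCC and T-cell volumes in 7.7 are no evidence about red-top size, because those draws use other containers.

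Second, 7.3.4 and 7.3.6 limit the NK/ADCC and T-cell draws to selected subjects, and without them most readings comply. That also stands, but 7.7 makes its claim for full participation and counts that 130 ml.

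Third, the most favourable reading is only 5 ml over the cap at 50 kg. True, but it takes one tube where the row prints two, and it omits footnote 4's late day-3 draws. With those draws added (6 tubes, 60 ml), the same merging gives 500 ml, or 10.0 ml/kg.

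Fourth, practical harm is limited. The draws are spread over about two months, and 7.7 withholds the next course while hemoglobin is below 10 gm/dl. This mitigates the risk but does not correct the stated volume.

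A reader might also infer a plain addition error from 400 against 430. The broken table does not support that, since a line may have been lost in extraction.

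**Conclusion.** The point holds as an inconsistency between sections with a conditional safety consequence. Section 7.7's PK and serology allowance cannot contain footnote 4's PK samples at the 10 ml tube specified elsewhere. With 10 ml red-tops and full participation, Table 7A needs about 440 to 490 ml, or 550 ml with all of footnote 4, against 430 ml stated. That is 8.8 to 11.0 ml/kg at 50 kg, and 8.9 to 11.3 at 45 kg after the 40 ml cut, against 8.7. The limit is met under 7.4.1's schedule or with the smaller draws in step 6 of the working.

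The match of 190 ml to 7.4.1 suggests that 7.7 was not updated for the day-2 and late draws. It does not prove it, because it depends on how shared tubes are counted.

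One side issue is secondary. Table 7A footnote 7, under which "the volumes of these syringes will be reduced to 10 ml", is also attached to the baseline syringe, so the low-weight cut could be 80 ml. At 45 kg that brings the most favourable reading within the limit ((440 − 80)/45 = 8.0) but not the tube row (410/45 = 9.1) or full footnote 4 (470/45 = 10.4).

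**What to change.** Adopt one PK schedule and one stated red-top draw volume in 7.4.1, Table 7A with footnote 4, Table 7B and 7.7. Say how the pediatric-tube sentence applies to PK samples. Recompute the 7.7 lines, the total, and the 50 kg and 45 kg statements from that schedule, and state whether footnote 7 cuts the baseline syringe.

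If the late draws stay, cap the red-top volume at about 6.5 ml for full footnote 4 (about 7.9 ml if only the tube row is kept) and lower the 5 ml serum requirement to match. Otherwise drop late time points until 8.7 ml/kg holds down to 45 kg. At 10 ml per tube, with the 40 ml cut and no merged draws, 221.5 ml allows 22 tubes, so all 12 late tubes in the two courses would have to go (34 − 12 = 22). Raising the weight cut-off should wait until schedule and volume are settled.

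The cost is a corrected table and footnotes, and possibly smaller tubes or fewer PK time points. The efficacy analyses are unaffected.
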